### A2. Specific Aims and Hypotheses

In the planned trial, 90 individuals with heterogeneous chronic pain who are at risk for opioid misuse will be randomly assigned to telehealth-delivered CT, MM, or AS. Mechanisms and outcomes will be assessed with actigraphy, twice daily EMA, and weekly telephone interviews during baseline, treatment, and for 4-weeks post-treatment. Mechanisms of longer-term maintenance of gains will be evaluated at 3- and 6-month follow-up. Given past research showing equivalent efficacy for active treatments, we expect no significant group level outcome differences between conditions. However, we do expect *individual* variability in treatment response and maintenance of gains that will allow us to examine mechanisms of change. This study will address two aims.

#### A2a. Primary Aim and Hypotheses

**Aim 1: Test the LA&E model to investigate theory driven moderators of response to CT, MM, and AS.**

To accomplish Aim 1, we will use omnibus groups regions of significance (OGRS) tests to evaluate the effect sizes associated with the extent to which baseline pain catastrophizing, mindfulness, and activity level are respectively associated with reductions in opioid use following CT, MM, and AS.

**Hypothesis 1a:** Higher baseline levels of catastrophizing will be associated with greater reductions in opioid use in response to the CT intervention compared to MM or AS.

**Hypothesis 1b:** Lower baseline levels of activity will be associated with greater reductions in opioid use in response to AS compared to CT or MM.

**Hypothesis 1c:** Higher baseline levels of non-judgment will be associated with greater reductions in opioid use in response to MM compared to CT or AS.

**Aim 2: Examine the mediators underlying the expected change in opioid use during treatment.**

To accomplish Aim 2, we will use PROCESS bootstrap mediation models to evaluate the extent to which early treatment changes in the primary mechanisms (pain intensity and emotional distress, i.e., depression and anxiety) will predict subsequent late-treatment changes in opioid use (primary outcome), and the extent to which these associations are shared across the three treatments, or if some are unique to one or a subset of treatments.

**Hypothesis 2a:** If changes in pain intensity and emotional distress are mechanisms shared by CT, MM, and AS, then changes in opioid use in all three treatments will be predicted to approximately the same extent by changes in the primary mechanisms.

**Hypothesis 2b:** If changes in the primary mechanisms are *specific* to one (or a subset) of the three treatments, then Treatment Group X Assessment Period interactions will reveal that late-treatment changes in opioid use will be substantially and uniquely predicted by early-treatment changes in the primary mechanism(s) in one (or a subset) of the three conditions only.

We also predict that change in the mechanism variables will precede and predict change in outcome, but not vice versa.

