However, in terms of the *mechanisms specifically underlying the outcome of reduced opioid consumption in at risk populations*, there may be defining aspects of changes occurring during treatment that function as mechanisms unique to this population (that is, that do not mediate outcome in populations *not* at risk for opioid misuse). Specifically, given research that has shown a complex interaction between both pain intensity and emotional factors as drivers of opioid use within chronic pain populations, it is plausible that treatment related changes in both pain intensity as well as emotion (e.g., anxiety, depression) might be mechanisms specifically underlying reduced opioid consumption in individuals with chronic pain who are at risk for opioid misuse. Our pilot data from a randomized controlled trial (RCT) comparing CT, Hypnosis, and Hypnotic-CT in a musculoskeletal pain sub-sample provide preliminary support for the premise that treatment-related changes in pain intensity and depression might be critical mechanisms underlying reductions in opioid use. In this pilot data, pre- to mid-treatment changes in these mechanisms evinced significant, large associations with later (i.e., mid- to post-treatment) changes in opioid use ( $rs$  of .58 and .68 for intensity and depression, respectively) across individuals prescribed opioids at baseline ( $N=18$ ). Further, early changes in opioid use were not significantly correlated with later changes in intensity or depression ( $rs$  of -.22 and -.13 for intensity and depression, respectively). These lagged mechanism associations underlying treatment-related reduced opioid use were even larger in those individuals ( $N=9$ ) who at baseline met criteria for at risk opioid use ( $rs$  of .69 and .94 for intensity and depression, respectively). Thus, this pilot data supports the potential mechanism role of treatment related changes in pain intensity and depression as drivers of reduced opioid use in at risk groups.

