## **D6p. Study Data**

We list the demographic and descriptive information we propose to collect from the study participants in the next paragraph. The outcome variables, covariates (variables to control for in planned analyses if needed), and mechanism (mediator and moderator) variables for this study are listed in Table 3. Specific measures by time point are provided in Table 4.

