in pain intensity when assigned to MBCT ( $r = -.36$ ; within condition effect), with the boundary of significance identified as a Pain Catastrophizing Scale score of  $\leq 16.35$ ; (2) a further interaction effect for MM vs. MBCT ( $b = -.23$ ,  $p = .05$ , CI:  $-.46$  to  $.003$ ), showing that higher baseline mindfulness was associated with greater improvement in pain intensity in MBCT ( $r = .40$ ; within condition effect), with the boundary of significance identified as a Five Facet Mindfulness Questionnaire Observe Scale score of  $> 15.03$ . Thus, based on these effects in our pilot work testing the LA&E predictions, we anticipate that the proposed sample size for this supplemental project of  $N=90$  will be sufficient to detect medium to large effects (at the  $\alpha < .05$  level). Hypotheses 1a-1c would be supported if an interaction effect emerges (significant at the  $\alpha < .05$  level) and one or more of the within group effect sizes (of the moderator on the primary outcome) are medium or large.

*For Aim 2 of this supplemental study*, the primary mediator measures are: (1) a Numerical Rating Scale assessing characteristic pain intensity (in the past week); (2) the PROMIS Depression scale; and (3) the PROMIS Anxiety scale. Additional secondary mediators, selected per the primary mechanisms examined in the parent study (e.g., catastrophizing, mindfulness, activity level), will also be explored in the supplemental project sub-sample. The association between treatment-related changes in the primary mechanisms on changes in outcome will be tested via three PROCESS tests with 5,000 bias-corrected bootstrap resamples. The PROCESS bias-corrected bootstrap approach has been shown to consistently be the most powerful test of mediation (i.e., compared to the Sobel test, Baron and Kenny's approach) and is appropriate for small sample sizes. We will examine the significance of each path to determine if treatment condition has a differential effect on the mediator and/or outcome (although treatment-related differences in outcome are not expected), and whether early change in the mechanism is associated with later change in outcome. In the instance of a possible specific vs. shared mechanism effect, post-hoc associations will be tested via correlations to identify estimates of effect sizes for descriptive purposes.

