We applied this approach to the three active treatments in pilot data obtained in our RCT comparing CT, Hypnosis and Hypnotic-CT (within the subsample of participants who reported musculoskeletal pain who were prescribed opioids,  $N=18$ ) to examine the relative statistical power achieved in that sample to detect medium to large effects for the analyses planned for this supplemental project. In two PROCESS models testing if early change in pain intensity or depression were specific vs. shared mechanisms in accounting for late treatment change in opioid use, results showed: (1) a non-significant effect of condition on outcome (path *c*) as well as on both mechanisms (path *a*); and (2) a significant effect of both mechanisms on the outcome (path *b*;  $ps < .01$ ). Post-hoc correlations were then conducted for descriptive purposes. We found that early change in both pain intensity and depression were significantly associated with later change in opioid use across groups ( $rs = .58$  and  $.68$ , respectively); on the other hand, early change in outcome was not significantly associated with later change in mechanism. Taken together, these results (1) provide support for early change in pain intensity and depression as underlying later reductions in opioid use, and (2) are consistent with a shared mechanisms account for the role of early change in pain intensity and depression as mechanisms driving decreased opioid use across the treatments studied in this pilot data. The proposed sample size and procedures of the supplemental project will afford the capacity to test these associations more definitively.

Overall, our pilot data indicate that if changes in outcome and mechanisms in the supplemental project are medium to large in nature, then the sample size of  $N=90$  will be adequate to test the mediation hypotheses 2a and 2b. Support for Hypothesis 2a and the shared mechanisms conceptualization would be found in the instance of a non-significant effect

of condition on the mechanism variable, but significant ( $\alpha \leq .05$ ) effect of the mechanism on outcome collapsed across groups. Support for Hypothesis 2b on the other hand would be found in the instance of a significant effect of condition on the mechanism, with change in the mechanism differentially associated with change in outcome across treatment conditions.

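### Aim 2 predicts that mechanism change leads opioid change and not the reverse, but the planned models omit early opioid change and specify no test of direction

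*Protocol*

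**What the plan says.** Protocol section A2a, under Aim 2, predicts that early-treatment change in pain intensity and emotional distress will predict late-treatment change in opioid use, and then adds: "We also predict that change in the mechanism variables will precede and predict change in outcome, but not vice versa". Section I of the protocol also promises findings on the temporal sequence of lagged mechanism effects.

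Section D6s says the association will be "tested via three PROCESS tests with 5,000 bias-corrected bootstrap resamples". The paths to be examined are condition to mediator, condition to outcome, and "whether early change in the mechanism is associated with later change in outcome". Hypothesis 2a is supported by a non-significant condition effect on the mechanism together with a significant "effect of the mechanism on outcome collapsed across groups". Hypothesis 2b requires a condition effect on the mechanism and a mechanism–outcome association that differs by condition.

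D6s names no covariate for these models. D6p refers to Table 3 for covariates, but Table 3 as available has no covariate row. D6n provides only for covariates that emerge from comparing dropout between arms.

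The reverse direction appears only in the pilot (N=18). Section B1 reports that "early changes in opioid use were not significantly correlated with later changes in intensity or depression", and D6s repeats that "early change in outcome was not significantly associated with later change in mechanism".

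The SAP analyses categories of MME change with a chi-square test and secondary outcomes with ANOVA. It contains no mediation, lagged or directional analysis.

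**The concern.** Two things are missing, and they do different damage.

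First, early MME change is not in the forward models. Suppose pain or mood improves in the same weeks in which MME falls, and people who begin reducing go on reducing. Early mechanism change then correlates with late MME change only because both are tied to early MME change. The path is significant and reads as a lagged mechanism although nothing lagged has happened. This bears on Hypothesis 2a, because its support rule uses that path.

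Second, the prediction that the reverse does not hold has no specified analysis. The only precedent is the pilot, where the forward correlations were significant and the reverse ones were not. A significant result beside a non-significant one is not a test of the difference between them. If the trial repeats that reading, a chance split of p-values could be reported as a direction.

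**Working it through.** **1. The pilot figures (sections B1 and D6s, N=18).** The test is t = r√(16/(1−r²)) on 16 df. The 95% CI is tanh(atanh r ± 1.96/√15).

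| Direction | r | p | 95% CI |
|---|---|---|---|
| Forward, intensity | .58 | .012 | .16 to .82 |
| Forward, depression | .68 | .002 | .31 to .87 |
| Reverse, intensity | −.22 | .38 | −.62 to .28 |
| Reverse, depression | −.13 | .61 | −.56 to .36 |

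The significant and non-significant labels reproduce. The reverse intervals still allow large effects.

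Forward and reverse can be compared by Fisher z, treating the correlations as independent (an approximation), with SE √(2/15) = .365:
- Signed, intensity: (.662 + .224)/.365 = 2.43, p = .015.
- Signed, depression: (.829 + .131)/.365 = 2.63, p = .009.
- By absolute size, intensity: (.662 − .224)/.365 = 1.20, p = .23.
- By absolute size, depression: (.829 − .131)/.365 = 1.91, p = .06.

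**2. Bias in the forward path.** The sample sizes are the protocol's: 90 enrolled, and 90 × (1 − 0.20) = 72 with complete data. Let ρ be the correlation of early mechanism change with early MME change, and φ the correlation of early with late MME change. Neither is given in the documents; .3 to .5 is an assumed range. With no lagged effect, the correlation between early mechanism change and late MME change is ρφ. The two-sided rejection rate is about Φ(atanh(ρφ)√(n−3) − 1.96), plus a small opposite tail. For example, with ρ = φ = .5 and n = 72: .255 × 8.31 = 2.12, and Φ(0.16) = 56%.

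| ρ | φ | ρφ | n=72 | n=90 |
|---|---|---|---|---|
| .3 | .3 | .09 | 12% | 13% |
| .3 | .5 | .15 | 24% | 29% |
| .5 | .3 | .15 | 24% | 29% |
| .5 | .5 | .25 | 56% | 66% |

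Simulation with condition indicators in the model agrees to within about a point. Over repeated runs the ranges are about 11% to 56% at n=72 and 13% to 67% at n=90.

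**3. With early MME change in the model.** The numerator of the partial correlation is ρφ − ρφ = 0, and simulated rejection is about 5%. This holds because observed early MME change carries the whole confound in this model.

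**4. Zero or negative persistence.** With φ = 0, ρφ = 0 and rejection is about 5% without adjustment. Early and late change share the mid-treatment MME value, so measurement noise pushes φ downwards. With φ between −.3 and −.5, rejections in the hypothesised direction occur in under 0.5% of trials.

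A real effect can then be hidden. Take a true standardised path of .3, ρ = .3 and a persistence path of −.5. The unadjusted correlation is .3 + .3 × (−.5) = .15, and power at n=90 is about 29%. The residual variance is 1 − (.09 + .25 − .09) = .75. The partial correlation is .286/√(.082 + .75) = .31, and power is about 85%.

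**5. Shared latent improvement.** Suppose one latent trend drives all three changes, loading equally on early and late MME change. Early mechanism change then correlates ρ with both. The partial correlation is ρ(1−φ)/√((1−ρ²)(1−φ²)):
- Lowest case (ρ = .3, φ = .5): .15/.826 = .18.
- Highest case (ρ = .5, φ = .3): .35/.826 = .42.

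Even after adjustment, rejection is about 33% to 96% at n=72 and 40% to 99% at n=90.

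**6. Direction by p-value split.** In simulation with fully symmetric truth, no lagged effect and non-zero persistence, the forward-significant, reverse-non-significant pattern occurs in about 5% to 20% of trials for a given mediator.

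**The case against.** The defence has real substance.

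- **Direction is not the Aim 2 decision rule.** A reader might infer that temporal precedence is the whole Aim 2 conclusion. The support rules in D6s concern shared versus specific mechanisms, and neither uses direction. Direction is an additional stated prediction.
- **The plan is silent; it excludes nothing.** A reader might infer that a reverse analysis is ruled out, or that a split of p-values is the stated criterion. Neither is written. The pilot is described as the same approach and includes reverse correlations, so a reverse check is implied. It is unspecified, and as done in the pilot it would neither adjust for early opioid change nor compare directions.
- **The early and late windows already give time order.** They order the measurements but do not remove the confounding in step 2.
- **The pilot is not merely a chance split.** With signs kept, the two directions differ at approximate p = .015 and .009. By absolute size the difference is unclear (p = .23 and .06), and N=18 is small.
- **The inflation is conditional.** It needs both concurrent change and positive persistence.
- **Adjustment is not a complete cure.** A reader might infer that the covariate restores a 5% error rate in general. Step 5 shows that it does not for a participant who is simply improving on everything.
- **A mandatory difference test is debatable.** With a true forward correlation of .30 and reverse of 0, its approximate power is Φ(.3095/√(2/69) − 1.96) = 44% at n=72 and Φ(.3095/√(2/87) − 1.96) = 53% at n=90. A difference that excludes zero would still not show that the reverse effect is absent.

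All of this limits the size of the point. None of it supplies the missing covariate or the missing reverse analysis.

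**Conclusion.** The point stands in limited form. The protocol predicts one direction and excludes the other, but it plans only forward models, with no early MME change covariate, no specified reverse model and no rule for direction. The SAP does not fill the gap. Followed as written, the plan can report concurrent change as a lagged mechanism.

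The rates of 11% to 56% (n=72) and 13% to 67% (n=90) rest on assumed concurrent correlation and positive persistence of .3 to .5, with no true lagged effect. They illustrate what could happen and do not predict this trial's data. With zero persistence the problem disappears, and with negative persistence it works against the sponsor's hypothesis. The return to about 5% after adjustment depends on the model. This is a worthwhile and inexpensive improvement to a stated prediction; it does not show that Aim 2 as a whole is invalid.

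**What to change.** In D6s and the SAP:

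1. Include early MME change (pre- to mid-treatment, the window used in the pilot) as a covariate in each of the three forward models.
2. Fit the three mirror models: early MME change to late mechanism change, adjusting for early mechanism change. The weekly calls already collect MME, pain intensity, depression and anxiety.
3. Report both standardised paths and their difference with confidence intervals, and state that direction will not be inferred from one significant and one non-significant result.
4. State that the adjustment removes confounding through observed early MME change only, and not through a shared latent improvement trend.

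If the team prefers not to do this, it should drop the clause excluding the reverse direction and describe the result as a lagged association.

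The cost is one degree of freedom per model, three extra models and no new data. The SAP is dated July 2024, is written in the past tense and has no Aim 2 analysis, so this needs a new section that may have to be labelled post hoc. Directional claims will be harder to make.

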**A2b. Secondary Aim and Hypotheses**

We will test these baseline characteristics as moderators of long-term response at 1-, 3-, and 6-month follow-up as a secondary analysis.

As a further secondary aim, this study will also evaluate the post-treatment mechanisms that explain relapse, maintenance, and continued gains associated with these treatments. The Shared (Hypothesis 2a) and Specific (Hypothesis 2b) Mechanisms Models will also be applied to data collected via EMA and ActiGraph daily during the 4-weeks post-treatment to better understand the post-treatment mechanisms that underlie maintenance of gains and relapse.

**Exploratory Hypothesis 3a:** The Shared Mechanisms Model hypothesizes that if early post-treatment changes in pain intensity and emotional distress are shared maintenance mechanisms across the three treatments, then treatment condition will have small and non-

significant effects on early post-treatment changes in the mechanism variables (i.e., the effects of the three treatments on the mechanism variables early post-treatment will be similar; Shared Mechanisms Model).

**Exploratory Hypothesis 3b:** If early post-treatment changes (i.e., post-treatment to 2-weeks post-treatment) in pain intensity and emotional distress are *specific* to one of the three treatments, then Treatment Group X Assessment period interactions will identify that early post-treatment changes in one or more of the mechanisms will be significantly associated with late post-treatment changes (i.e., 2-weeks post-treatment to 4-weeks post-treatment) in opioid use (Specific Mechanisms Model).

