## **D5. Participants**

We propose to enroll 90 participants. The anticipated lost to follow-up rate for this study is 20% of the total enrollment number, or 18 participants. We anticipate that with 90 participants enrolled (although we may elect to continue to enroll beyond this if we have the resources to do so, as this would provide even more power for the planned analyses) and a 20% attrition rate, we will have complete data for 72 of our participants; the primary analyses are to be conducted with the intent to treat sample.

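### The Shared Mechanisms Model is supported by a non-significant condition effect, with no margin or confidence-interval criterion, so imprecision can count as evidence of similarity

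*Protocol*

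**What the plan says.** Protocol D6s (Aim 2) gives the only explicit support rule for the shared model: "Support for Hypothesis 2a and the shared mechanisms conceptualization would be found in the instance of a non-significant effect" of condition on the mechanism variable, together with a significant "effect of the mechanism on outcome collapsed across groups". No size criterion is attached to the condition effect.

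Protocol A2b extends this to the post-treatment period: "The Shared (Hypothesis 2a) and Specific (Hypothesis 2b) Mechanisms Models will also be applied to data collected via EMA and ActiGraph daily". Exploratory Hypothesis 3a then predicts that, if the mechanisms are shared, "treatment condition will have small and non"-"significant effects on early post-treatment changes in the mechanism variables", and explains this as meaning that "the effects of the three treatments on the mechanism variables early post-treatment will be similar; Shared Mechanisms Model". *Small* is not quantified.

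The SAP covers categories of opioid-dose change and mean changes in secondary outcomes. It contains no mediation or mechanism analysis, no margin, and no rule for declaring arms similar.

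**The concern.** *Similar* and *shared* are positive claims about how close the arms are. The evidence offered for that part of the claim is the failure of an ordinary test of difference, and such a test fails more often when the sample is smaller, dropout is higher or the scale is noisier. A rule of this form therefore makes the shared conclusion easier to reach as the data get worse, at least as far as the condition effect is concerned.

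Shared versus specific mechanisms is the question Aim 2 asks, and A2a lists Aim 2 under the primary aim. D6s already reads pilot data in this way. With 18 people across three treatments, about six per arm if equally split, a non-significant condition effect plus a significant mechanism effect was taken as consistent with a shared account. Six per arm says almost nothing about whether the treatments moved the mechanism equally.

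**Working it through.** **Inputs from the Protocol.** D5: 90 enrolled and 20% lost, so 90 × (1 − 0.20) = 72 with complete data, which reproduces the plan's figure. D6k: equal chance of each of three conditions, so 90/3 = 30 or 72/3 = 24 per arm. D6s: alpha .05, stated there for the mechanism-to-outcome effect.

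**Assumptions not in the documents.** A two-sided alpha of .05 also applies to the condition effect; one arm differs from the other two by 0.5 SD of the change score; one change score per person; omnibus F test. D6s says N = 90 is adequate for medium to large effects but gives no power, SD or numeric effect, so that statement cannot be reproduced.

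**1. The test alone.** Arm means are 0, 0 and 0.5 SD, with grand mean 0.167. The squared deviations sum to 0.028 + 0.028 + 0.111 = 0.167. Noncentrality = n × 0.167, which is 4.0 at 24 per arm and 5.0 at 30. With 2 and 3n − 3 degrees of freedom:

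| True pattern and criterion | 24/arm | 30/arm |
|---|---|---|
| One arm off by 0.5 SD, F non-significant | 60.0% | 51.1% |
| Arms at 0, 0.25, 0.5 SD, F non-significant | 69.1% | 61.9% |
| One arm off, all three unadjusted pairwise tests non-significant | 43.4% | 35.0% |

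The figure depends on the configuration, but under all three the chance of a non-significant result is large.

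**2. What a non-significant result leaves open.** The 95% CI half-width for a pairwise difference is t(.975, 2n − 2) × √(2/n), which is 0.58 SD at 24 per arm and 0.52 SD at 30. Even an observed difference of exactly zero leaves a true difference of 0.5 SD inside the interval.

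**3. The two-leg 2a rule.** With the same 0.5 SD difference and an assumed within-arm mechanism–outcome correlation of .3 to .5, simulation gives both legs met in about 44% to 59% of trials at 24 per arm and 42% to 51% at 30 (good to about a percentage point). The second leg filters little, because a real slope of that size usually passes it.

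**4. Hypothesis 3a, which also requires *small*.** Reading *small* as a ceiling on the largest observed gap between arms, in addition to a non-significant F:

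| Ceiling on largest gap | 24/arm | 30/arm |
|---|---|---|
| 0.2 SD | 4.1% | 3.4% |
| 0.35 SD | 14.4% | 13.4% |
| 0.5 SD | 32.3% | 32.9% |

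The undefined word moves the rate about tenfold, from 3% to 33%.

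**5. Could similarity be shown at this size?** If the arms are truly identical, all three pairwise 90% CIs fall inside ±0.5 SD in 1% of trials at 24 per arm and 5% at 30, and inside ±0.8 SD in 49% and 68%. A single pairwise equivalence test with a 0.5 SD margin and 80% power needs 2 × ((1.645 + 1.282)/0.5)² ≈ 69 per arm.

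**The case against.** Several objections have force.

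- **3a is conditional and has two parts.** It states what the model predicts and requires effects to be small as well as non-significant. A reader might infer that 3a would report *similar* in 51% to 60% of trials. The text does not support that: the figure is the non-significance rate and therefore an upper bound for that test configuration. This stands, and it is why D6s, where *small* does not appear, is the main target.
- **Shared is defined by association.** Hypothesis 2a in A2a says a mechanism is shared if its change predicts opioid change to about the same extent in all three treatments. Arms can differ in mean mechanism change and still satisfy that. So a reader who counts every shared verdict at a 0.5 SD difference as false goes too far. What remains is that D6s makes non-significance part of the support, and that inference is unsound whether or not the mechanism is in fact shared.
- **2a and 2b are not two sides of one test.** Hypothesis 2b also needs differential association, and 2a needs its second leg. This is correct and is allowed for in the two-leg figures.
- **The inputs are assumed.** The 0.5 SD, the single deviant arm and the omnibus test are not in the Protocol, and A2b refers to daily data whereas the calculation uses one score per person. The percentages are illustrative; the flaw in the inference does not depend on them.
- **3a is exploratory.** This limits the consequence for 3a, but not for 2a.

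**Conclusion.** The D6s rule is wrong as written: it takes failure to detect a difference between arms as positive evidence for the shared model, and no margin or interval criterion in either document corrects it. Exploratory Hypothesis 3a has the same weakness in milder form. It adds *small* but leaves the word open to definition after the data are seen, and its exploratory status limits the severity there.

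On the stated assumptions, the condition test is non-significant in about 51% to 60% of trials and the full 2a rule is met in about 42% to 59%. For 3a the rate is about 3% to 33% if *small* means a largest observed gap below 0.2 to 0.5 SD. These figures show how little a non-significant result establishes at this sample size. They are not rates of false shared-mechanism conclusions.

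**What to change.** In D6s (Hypothesis 2a) and A2b (Hypothesis 3a), and in a mechanism section added to the SAP:

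1. Report each pairwise between-arm difference in early mechanism change with its confidence interval. D6s already commits Aim 1 to interpretation through point estimates and intervals.
2. Report a non-significant condition effect as inconclusive, not as support for the shared model and not as *similar*.
3. Claim similarity only if the intervals for all three pairwise differences lie inside a margin fixed before the mechanism results by arm are seen. The SAP is written in the past tense, so if those results have already been seen, items 1 and 2 should stand alone.

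This changes wording only and needs no new data or participants. The cost is that, with 72 to 90 participants, similarity will rarely be shown at a 0.5 SD margin and only about half to two-thirds of the time at 0.8 SD, even if the arms are identical. *Inconclusive* will be a common verdict, and the report should say that the sample size is the reason.
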